10.3. FOOD ALLERGY QUALITY OF LIFE SCORES (FAQLQ, FAQL-PB, FAIM)

The questionnaires will be administered to subjects at the visits indicated in the schedules of events in the appendices of the protocol. The questionnaires should be completed before in-clinic dosing. The questionnaires may be completed during the observation period after completion of peanut protein administration as part of the OLFC.

Subjects may also be asked to complete health-related QoL questionnaires during the 1year follow-up observation period.

FAQLQ

The FAQLQ are questionnaires that measure health-related QoL in patients with food allergy. The following versions of the FAQLQ forms have been developed.

- Children 8 to 12 years of age (FAQLQ-CF) (Flokstra-de Blok, 2009)
- Adolescents 13 to 17 years of age (FAQLQ-TF) (Flokstra-de Blok, 2008)
- Adults 18 years of age and older (FAQLQ-AF) (van der Velde, 2009)
- Parents/caregivers of allergic children (FAQLQ-PF) (DunnGalvin, 2008)
- Parents/caregivers of allergic teenagers (FAQLQ-PFT)

Each subject or parent/caregiver should complete the same version of the form completed in the parent study, regardless of current age.

For subjects aged ≤ 12 years, the parent/caregiver will complete the FAQLQ-PF. For subjects completing the FAQLQ-CF, subjects and parents/caregiver should be instructed to have the child provide his/her own responses. The parent/caregiver can help read the question or explain the meaning of the question, but the response should be selected only by the child.

The questionnaires include 4 domains common to each (allergy avoidance, dietary restrictions, emotional impact and risk of accidental exposure), and the adult form also includes a food allergy related health domain. The number of items ranges from 23 to 29. Each item is scored on a 7-point scale from 0 (no impact) to 6 (extreme impact).

The total score is the arithmetic average of all non-missing items. Domain scores are calculated similarly. If less than 80% of the items are complete, then the total score will not be calculated. Similarly, if less than 80% of the items within a domain are complete, then the domain score will not be calculated.

FAQLQ questionnaire scores will be listed by treatment pathway and subject ID.

FAQL-PB

The FAQL-PB is a 17-item self-administered questionnaire that measures QoL in caregivers for children with food allergy (Cohen, 2004). Each of the 17 questions is a 7-point Likert item, and the index is scored as a summated rating scale, with a higher FAQL-PB score indicating a worse QoL. Two domain scores will be calculated (life limitations and emotional stress).

The total score is the arithmetic average of all non-missing items. Domain scores are calculated similarly. If less than 80% of the items are complete, then the total score will not be calculated. Similarly, if less than 80% of the items within a domain are complete, then the domain score will not be calculated.

A listing of the raw scores as recorded in the CRF will be provided, sorted by treatment pathway and subject ID.

FAIM

The FAIM questionnaires were developed to measure construct validity of the FAQLQ. The FAIM questionnaires consist of 4 to 8 questions and measure the subject's perception of disease severity and their expectation of allergen exposure outcome. The FAIM may be used within a study to check the construct validity of the FAQLQ and explore changes in subject and parent/caregiver expectation of outcome (van der Velde, 2010). Each question is scored on a 7-point scale from 0 (low likelihood of a bad outcome) to 6 (extremely likely to have a bad outcome).

FAIM questionnaire scores will be listed by treatment pathway and subject ID.

11. ANALYSIS OF EXPLORATORY ENDPOINTS

11.1. PEANUT-SPECIFIC AND PEANUT COMPONENT-SPECIFIC IGE AND IGG4

Blood samples to measure ps-IgE, ps-IgG₄ levels, and total IgE levels will be collected at the timepoints as indicated in the schedules of events in the appendices of the protocol.

Ps-IgE/IgG₄ ratio will be calculated, listed by subject, and summarized by visit and treatment group (AR101). Results outside the limits of quantification will be displayed as less than the lower limit of quantification (LLOQ), or greater than the upper limit of quantification (ULOQ), as appropriate. These values will be summarized as either the LLOQ or the ULOQ. If the ps-IgE or ps-IgG₄ is outside of the limits of quantification, the ps-IgE/IgG₄ ratio will be calculated using the LLOQ or ULOQ as appropriate.

Summary statistics, including geometric means and geometric standard deviations, will be presented by time point and years of total AR101 exposure including parent studies and overall separately for Treatment Pathways 1-3, 4, and 5.

Summaries of change from baseline to Study Exit visit for total IgE, ps-IgE, ps-IgG₄, ps-IgE/IgG₄ ratio, peanut-specific IgE and IgG4 components (Ara h 1, Ara h 2, Ara h 3, Ara h 8, Ara h 9) and the corresponding IgE/IgG4 ratio of each component will be presented using change calculated on the log₁₀ scale.

11.2. SKIN PRICK TEST

SPTs will be conducted at the visits indicated in the schedules of events in the appendices of the protocol. Results from the SPT will be listed by treatment pathway, subject ID, and visit, including test date and time, and measurements (in mm) of the following: peanut wheal (long axis), peanut wheal (short axis), saline wheal (long axis), saline wheal (short axis), histamine wheal (long axis), and histamine wheal (short axis).

A derived mean wheal diameter score will be calculated as the average of the long and short axis from the peanut wheal minus the average of the long and short axis from the saline wheal. Summary statistics for the derived SPT mean wheal diameter will be presented at each visit, for change from baseline to End of Treatment, and for change from baseline to Study Exit visit by years of total AR101 exposure including parent studies and overall.

11.3. TEST FOR RESPIRATORY AND ASTHMA CONTROL IN KIDS (TRACK) AND ECZEMA AREA AND SEVERITY INDEX (EASI)

TRACK and EASI scores are measured as indicated in the schedules of events in the appendices of the protocol.

TRACK

In Treatment Pathways 4 and 5, asthma control in subjects aged 1 to < 5 years with preexisting asthma will be assessed using TRACK scores and by the incidence of asthma rescue medication use. Subjects who turn age 5 years during the study or who are aged \geq 5 years at enrollment in Treatment Pathways 4 and 5 will be administered the C-ACT questionnaire instead of the TRACK questionnaire.

The TRACK questionnaire will be administered at the visits indicated in the schedules of events in the appendices of the protocol. The parent/caregiver is to complete the TRACK, a 5-item standardized questionnaire used to evaluate respiratory and asthma control in children aged < 5 years with symptoms consistent with asthma (Zeiger, 2011). Each item is scored on a 5-point scale from 0 (4 or more times a week) to 20 (not at all). Higher scores indicate better respiratory and asthma control.

EASI

For subjects with pre-existing eczema or atopic dermatitis in Treatment Pathways 4 and 5, the severity of clinical signs of eczema or atopic dermatitis will be assessed using the EASI scoring system. Higher scores indicate greater severity of eczema or atopic dermatitis.

A listing of the results from the TRACK and EASI questionnaires will be provided, sorted by treatment pathway, subject ID, and visit.

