5.9.3 Symptomatic Treatment for Chronic and/or Recurrent Adverse Events

Symptomatic treatment for chronic/recurrent AEs is permitted (except for prohibited medications [Section 5.9.5]) but should be used to supplement dose reduction, not substitute for it. It is advised that an attempt to withdraw symptomatic therapy be made prior to dose re-escalation. If unsuccessful, symptomatic therapy may be resumed and dose escalation may proceed with the symptomatic therapy in place.

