6.2.1 Skin Prick Test

SPTs will be conducted at the visits indicated in the Schedules of Events in the appendices and wheal measurements recorded in the source document. SPTs will be performed using procedures for food allergens approved by both study site and the sponsor. At the time that the SPT is performed, the subject must have taken no antihistamines or other medications that could interfere with the assessment of the SPT for an appropriate length of time (eg, 5 half-lives of the antihistamine that is being used or other medications in question).

An SPT probe is pressed through a commercial peanut allergen extract into the epidermis. Positive (histamine) and negative (saline-glycerin) controls are also injected into the epidermis to establish that the response is not blocked and to determine if there is dermatographism, respectively.

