3.3. EXPLORATORY ENDPOINTS

The exploratory endpoints are as follows:

- Change in peanut-specific (ps) and peanut component-specific serum immunoglobulin G subclass 4 (IgG4)
- Change in total, peanut-specific, and peanut component-specific serum immunoglobulin E (IgE)
- Change in peanut skin prick test (SPT) mean wheal diameter
- Change in Test for Respiratory and Asthma Control in Kids (TRACK) and Eczema Area and Severity Index (EASI) scores

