7.4. DATA DERIVATIONS AND DEFINITIONS

The following definitions and derivations will be used throughout this study:

- Study Day is calculated as (assessment date date of first dose of AR101 in ARC008 + 1) for assessments and visits performed on or after the date of first dose of AR101 in ARC008, and (assessment date – date of first dose of AR101 in ARC008) for assessments and visits prior to the date of first dose of AR101 in ARC008. There will therefore be no Study Day 0.
- Baseline is defined as the last non-missing value prior to the first dose of AR101 in ARC008.
- Change from baseline is calculated as observed value after the first dose of AR101 in ARC008 baseline value.
- A duration expressed in months will be calculated by dividing the duration in days by (365.25 / 12).

• A duration expressed in years will be calculated by dividing the duration in days by 365.25.

The study periods are defined in Table 4 (used to create the study period flags) with the first and last dose dates for each study period being identified as follows:

Study Period	Treatment Pathways	First Dose Date	Last Dose Date
Initial Escalation	3 and 5	Date and time of first in-clinic dose at Initial Escalation Day 1	Date of latest in-clinic dose at Initial Escalation Day 1 or Day 2. Set the time to be 23:59 and 59 seconds on each of these respective days.
Up-Dosing	2	For subjects that do not undergo Repeat Up-Dosing: the date and time of first in-clinic or at home dose of treatment in ARC008 if prior to date of first Initial Maintenance Visit. For subjects that undergo Repeat Up- Dosing: the date repeat up-dosing (Treatment Pathway 2) was started.	Date of first in-clinic dose of 300 mg during the Up-Dosing period. For subjects who do not reach the 300 mg dose: the latest of the last in-clinic dose during the Up-Dosing period or the date of last dose at home. Set the time to be 23:59 and 59 seconds on the respective day.
	3 and 5	The day following the date of last in- clinic dose at Initial Escalation Day 2	Date of first in-clinic dose of 300 mg during the Up-Dosing period. For subjects who do not reach the 300 mg dose: the latest of the last in-clinic dose during the Up-Dosing period or the date of last dose at home. Set the time to be 23:59 and 59 seconds on the respective day.
Initial and Extended	1 and 4	Date and time of first in-clinic or at home dose of treatment in ARC008	Date of last dose of study product

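### The SPT wheal score has no histamine-control validity rule, so a blocked skin test at any visit, baseline included, is summarized as a true small wheal

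*SAP*

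**What the plan says.** SAP 3.3 names the exploratory endpoint: "Change in peanut skin prick test (SPT) mean wheal diameter". SAP 11.2 derives it in two terms: "A derived mean wheal diameter score will be calculated as the average of the long and short axis from the peanut wheal", then "minus the average of the long and short axis from the saline wheal". The score is summarized at each visit, "for change from baseline to End of Treatment, and for change from baseline to Study Exit visit".

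The same section puts the positive control among the listed measurements ("histamine wheal (long axis), and histamine wheal (short axis") and does not use it again. Protocol 6.2.1 gives the reason for the controls: "Positive (histamine) and negative (saline-glycerin) controls are also injected into the epidermis to establish that the response is not blocked". The saline control is there to detect dermatographism.

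SAP 7.4 sets the reference value: "Baseline is defined as the last non-missing value prior to the first dose of AR101 in ARC008". It attaches no condition on the validity of the test. SAP 4 uses the Safety Population for every analysis, so no set of valid tests is defined elsewhere.

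On medication, Protocol 5.9.3 states: "Symptomatic treatment for chronic/recurrent AEs is permitted". Protocol 5.9.1 names H1 and H2 histamine blockers among the examples. Protocol 5.9 and 6.2.1 require antihistamines to be stopped before an SPT, with five half-lives as the guide, and exclusion criterion 12 in Protocol 4.2 removes subjects who cannot do this.

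**The concern.** The two controls answer different questions. Saline corrects for skin that reacts to anything. Histamine shows whether the skin can react at all. The SAP builds the first into the score and leaves the second in a listing. If the histamine response is absent, a near-zero peanut wheal says nothing about peanut sensitization, but the formula returns a near-zero score and the summary treats it as data.

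SAP 13 drops the change summaries for most other change endpoints (PEF, ACT and C-ACT, TNSS, tolerated dose, the quality-of-life scores, TRACK and EASI). SPT and the immunoglobulins keep theirs, so SPT change is one of the few change results the report will show. The SAP also has rules for unusable or out-of-range values elsewhere: item-completion minimums for FAQLQ, FAQL-PB and PEESS, a complete-response rule for ACT, and quantification limits for the immunoglobulins. SPT has a dedicated validity control and no corresponding rule.

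**Working it through.** The plan gives no expected SPT change, standard deviation or sample size, so there is no figure to reproduce. The check applies the SAP 11.2 formula to a blocked test.

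**Formula (SAP 11.2 and 7.4).** Score = (peanut long + peanut short)/2 − (saline long + saline short)/2. Change = later score − baseline score.

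**Single tests.** All millimetre values are assumptions. Take a true peanut wheal of 11 × 9 mm, saline 0 mm and no true change.

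| Baseline test | Later test | Scores (mm) | Change under the SAP (mm) |
|---|---|---|---|
| valid | valid | 10, 10 | 0 |
| valid | half blocked (5.5 × 4.5) | 10, 5 | −5 |
| valid | fully blocked | 10, 0 | −10 |
| fully blocked | valid | 0, 10 | +10 |

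All four rows enter the summary unmarked. The third and fourth show equal errors in opposite directions.

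**Group mean.** Let f1 and f0 be the shares of later and baseline tests that are blocked, s the fraction of the wheal suppressed, and W1 and W0 the true mean net wheals at those times. Assume that blocking is unrelated to wheal size. Then

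shift in mean change = −f1 × s × W1 + f0 × s × W0.

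With f0 = 0 and s = 1:

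| f1 | W1 = 8 mm | W1 = 12 mm |
|---|---|---|
| 2% | −0.16 | −0.24 |
| 5% | −0.40 | −0.60 |
| 10% | −0.80 | −1.20 |

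Half suppression (s = 0.5) halves each entry. With f0 = f1 and W0 = W1 the shift is zero. The sign therefore depends on whether blocking is more frequent at baseline or later, and the documents give neither rate.

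**Where an exclusion could occur.** SAP 7.1.3 selects among repeated values by closeness to the target month, not by validity. SAP 7.4 takes the last non-missing value as baseline. SAP 7.5 handles missing data only. SAP 5 can record a washout breach as a protocol deviation, but no deviation removes a value. None of these intercepts a blocked test. If a site repeated a blocked test and recorded both results, the window rule could still select the blocked one.

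**The case against.** A reader might infer that the error always favours AR101, because antihistamines are allowed for reactions during treatment and blocked tests would then cluster after a treatment-free baseline. The documents do not support this:

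- Baseline precedes the first dose in ARC008, not the first dose ever. Subjects in Pathways 1, 2 and 4 had already received AR101 in a parent study, so only Pathways 3 and 5 have a baseline before any AR101.
- Protocol 5.9 lets usual medication for asthma, rhinitis and atopic dermatitis continue throughout, so antihistamine use can exist at baseline too.
- The Study Exit visit falls about 12 months after the last dose, so reactions to ongoing treatment do not explain blocked tests there.

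It would also be too strong to say that the histamine data are thrown away. They are listed by subject and visit, and a reader could find failed controls by hand.

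The safeguards are real. Washout is mandatory, inability to comply is an exclusion, many SPT visits are also food-challenge visits with the same washout, and SAP 16 provides for checks on invalid records and outliers. Protocol 6.2 refers to a Study Procedures Manual that is not available here and may tell sites to repeat a blocked test. The median is reported beside the mean and would move little with a few near-zero values.

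All of this stands as a limit on frequency and importance. It does not supply the missing rule. The histamine control exists to catch washout failures, and the SAP refers to no operational rule that would keep such tests out of the summaries. Failures are plausible: Protocol 8.1.4.2 foresees subjects who stop AR101 for gastrointestinal events and cannot come off histamine blockers by 12 weeks, and early discontinuers have an SPT at the End of Treatment visit.

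**Conclusion.** The gap holds as a minor point. The SAP's derivation gives a misleading value for any blocked test, at baseline or later, and nothing in the SAP marks or counts these tests. The net direction and size cannot be determined from the documents. The 0.16 to 1.2 mm range rests entirely on assumed inputs: 2% to 10% of post-baseline tests fully blocked, all baselines valid, and a true wheal of 8 to 12 mm. The upper end needs frequent washout failure with complete suppression, which the safeguards make unlikely. Severity is low because the endpoint is exploratory, the study is descriptive, and no error rate or sample size depends on it.

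**What to change.** In SAP 11.2, treat the derived wheal as not evaluable when the mean histamine wheal minus the mean saline wheal is below a validity threshold. The sponsor should set and justify that threshold, consistent with the approved SPT procedure. Apply the rule to baseline and later tests alike, before the baseline value and the visit-window value are chosen, so that a valid neighbouring test can be used. Report the number of invalid tests by visit, and show the summaries with and without them.

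SAP 1.1 places Version 2 after database lock and restricts its changes to Appendix A. A rule added now would have to be labelled post hoc, which SAP 6.1 allows for additional exploratory analyses.

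The cost is one derivation rule, one count row and a second version of the summary. The measurements are already collected. The downside is slightly fewer evaluable tests. If few tests fail, the count supports the existing result.

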this protocol according to Good Clinical H Code of Federal Regulations (CFR) – 21 CH the International Council for Harmon Pharmaceuticals for Human Use Guide	the principal investigator, I agree to conduct Practice, as delineated in the United States FR Parts 50, 54, and 312 (Subpart D) and in hisation of Technical Requirements for eline for Good Clinical Practice E6, and protocol. Furthermore, I will conduct this enal, and international requirements.	
Principal Investigator (Print)		
Principal Investigator (Signature)	Date	

	Protocol ARC008 Synopsis		
Title	A Multicenter, Open-Label, Longer-Term Study of AR101 Characterized Oral Desensitization Immunotherapy in Subjects Who Participated in a Prior AR101 Study		
Short Title	Longer-Term Study of AR101	CODIT™	
Clinical Phase	3		
US IND	15463		
EudraCT	2017-001334-26		
Sponsor	Aimmune Therapeutics, Inc.		
Number of Subjects	The potential number of subject	ts who may be enrolled in this study is approximately 950.	
Purpose of Amendment 6.0	a sustained clinical effect after	dment is to modify the study design to demonstrate 5 years total of AR101 treatment including all prior on period after stopping AR101 treatment.	
Objectives and	Objectives	Endpoints	
Endpoints	Primary: To describe safety and tolerability during longer-term administration of AR101 and follow-up observation after the last dose of AR101	 Frequency of adverse events (AEs) Frequency of premature discontinuation of AR101 dosing due to AEs Frequency of premature discontinuation of dosing due to chronic/recurrent gastrointestinal (GI) AEs Frequency of AEs that lead to a change in treatment regimen Frequency of AEs that lead to early withdrawal Frequency of anaphylaxis (as defined in Section 8.1.4.1) Frequency of use of epinephrine as a rescue medication Frequency of accidental/nonaccidental ingestion of peanut and other allergenic foods Frequency of AEs following accidental/nonaccidental exposure to peanut and other allergenic foods Frequency of eosinophilic esophagitis (EoE) 	

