3.2.7 Follow-Up Observation Period (All Treatment Pathways)

The End of Treatment visit will be followed by a 12-month observation period. During observation, management of peanut allergy will be guided by the subject's physician.

ARC008 Protocol Amend 6.0

Observation assessments will be conducted by telephone at 3, 6, and 9 months to enquire about the following:

- Current treatment plan (eg, commercially available product, complete peanut avoidance, use of food equivalents for peanut oral immunotherapy, other investigational immunotherapy, other)
- Events of systemic allergic reactions, EoE, accidental/nonaccidental exposures to food allergens and their outcomes, use of epinephrine, hospitalizations (all causes), emergency department visits (all causes), and SAEs

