3.4 Study Design Rationale

3.4.1 AR101 Dose Regimen and Study Periods

The dose regimen in this study is based on the dosing regimen successfully used in the phase 2 studies, ARC001 and ARC002. The ARC001 dosing regimen was based on the work of the Consortium of Food Allergy Research (CoFAR) and its investigators. The basic structure of the dose regimen consists of a 2-day initial escalation at very low doses, followed by an up-dosing phase of dose escalations with a single dose level escalation occurring every 2 weeks, and then an initial maintenance phase followed by an extended maintenance phase. This dosing regimen was well tolerated and effective in previous studies (Burks, 2012), and the 300 mg target dose was well tolerated and had clinically important activity in the AR101 phase 3 studies.

In addition, the dosing regimen to be used in this study in the Maintenance and Extended Maintenance Periods is a 300 mg dose to be administered at the dosing interval that the subject last tolerated in a previous Aimmune-sponsored clinical study.

A follow-up observation period after the last dose of AR101 is included to assess sustained clinical effect of AR101 treatment.

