4.4.1 Criteria for Early Discontinuation

A subject who meets any of the following must discontinue dosing with AR101:

- 1. Pregnancy
- 2. Life-threatening symptoms (CoFAR grade 4; Appendix 9), including, but not limited to anaphylaxis resulting in hypotension, neurologic compromise, or mechanical ventilation secondary to peanut OIT dosing or any peanut food challenge
- 3. Severe allergic hypersensitivity symptoms (CoFAR grade 3; Appendix 9) that require intensive therapy (to be determined by the investigator but may include such interventions as IV epinephrine, intubation, or admission to an intensive care unit) or those that are recurrent. Subjects who experience severe symptoms (eg, severe nausea, rhinorrhea, or pruritus) that are not life-threatening, not requiring intensive therapy, and not associated with any other features indicating a serious clinical condition, and who the investigator feels are suitable to continue with the study, will be discussed with the medical monitor and may continue the study under close supervision if both the investigator and the medical monitor deem it appropriately safe to do so
- 4. Dose-limiting symptoms that occur at or before the 3 mg single dose on Initial Escalation Day 1 (Treatment Pathways 3 and 5 only)
- 5. Dose-limiting symptoms that occur on Initial Escalation Day 2 (Treatment Pathways 3 and 5 only)
- 6. Nonadherence: For subjects on a daily dose regimen, missing > 7 consecutive dosing days on any 1 occasion or missing 3 consecutive dosing days on 3 or more occasions during Up-Dosing, other than for treatment of an AE or a dispensing error
- 7. Extended dosing interruptions: For subjects on a daily dose regimen, any circumstances, including medical indications that require missed AR101 dosing for ≥ 15 consecutive days, with the exception of the voluntary 30-day hiatus for GI AEs
- 8. On 1 episode, failure to accomplish up-dosing to 300 mg AR101 daily after 3 attempts (Treatment Pathways 2 and 3 only)
- 9. On 1 dose-reduction episode, failure to identify a tolerated dose of AR101 after 3 attempts at dose reduction

- ARC008 Protocol Amend 6.0
- 10. Administration of more than 2 doses of epinephrine for the treatment of any single AR101-related allergic reaction
- 11. Subject desires to receive commercially available product

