5.9.5 Prohibited Medications

Use of the following medications is prohibited during the study, except during the follow-up observation period:

- Use of any therapeutic antibody or any other immunomodulatory therapy, including any other OIT or initiation of any new aeroallergen therapy
- Systemic corticosteroids used for longer than 3 consecutive weeks throughout the study (if used, subjects must not be up-dosed during the 3 days after the last dose of oral steroids)
- Oral beta-blockers
- Angiotensin-converting enzyme inhibitors
- Angiotensin-receptor blockers
- Calcium channel blockers
- Tricyclic antidepressants

During the study, subjects may be at increased risk for anaphylaxis, which in severe form can result in a drop in BP. Additionally, the administration of epinephrine to treat anaphylaxis can result in a sudden rise in BP. For these reasons, the risks accompanying the use of any medication with known cardiovascular side effects must be weighed against the potential benefits of peanut OIT. This assessment must be performed for any medications being taken at study entry or added during the study. The use of medication with known cardiovascular side effects during the study is discouraged; however, if an investigator deems such use necessary, it must be undertaken with caution. It is beyond the scope of this protocol to list all drugs with cardiovascular side effects. Classes of drugs with a high potential for cardiovascular side effects include antipsychotics, cyclooxygenase-2 inhibitors (chronic use), nonsteroidal anti-inflammatory drugs (chronic use), antiarrhythmics, antihypertensives, and antineoplastics. Before a drug with cardiovascular side effects is used in conjunction with OIT, the investigator should discuss its use with a medical monitor.

It is beyond the scope of this protocol to list all immunomodulatory drugs; broadly, these include drugs to treat or prevent transplant rejection, autoimmune disease, and certain neoplasias (eg, cyclosporine, tacrolimus, antitumor necrosis alpha drugs, and other anti-cytokine drugs), as well as other allergen immunotherapies. If an investigator contemplates the use of a potentially immunomodulatory drug during the study, the investigator should discuss this with a medical monitor.

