9.1 Sample Size

There is no sample size calculation for this study. The sample size will be determined by the number of eligible subjects from each of the prior AR101 studies who participate in this study.

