2.3. EXPLORATORY OBJECTIVES

The exploratory objectives of the study are:

- To evaluate effects on immunologic parameters after longer-term administration of AR101 and follow-up observation after the last dose of AR101
- To evaluate changes in control of pre-existing asthma or atopic dermatitis in subjects from prior study ARC005

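### The Study Exit skin prick and immunoglobulin summaries pool subjects who may still be on peanut immunotherapy with subjects who are not, so they cannot show the effect after stopping AR101

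*SAP*

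**What the plan says.** **Purpose of the follow-up year.** Protocol 3.4.1: "A follow-up observation period after the last dose of AR101 is included to assess sustained clinical effect of AR101 treatment". The exploratory objective behind the SPT and immunoglobulin endpoints (SAP 2.3) is "To evaluate effects on immunologic parameters after longer-term administration of AR101 and follow-up observation after the last dose of AR101". Study Exit falls about 12 months after the last dose (Protocol 3.2.8).

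**What subjects may take in that year.** Protocol 3.2.7 leaves management to the subject's physician and has sites ask by telephone about "Current treatment plan (eg, commercially available product, complete peanut avoidance, use of food equivalents for peanut oral immunotherapy, other investigational immunotherapy, other". The list in Protocol 5.9.5, which covers other oral immunotherapy and immunomodulators, opens with "Use of the following medications is prohibited during the study, except during the follow-up observation period". Exclusion criteria 5, 6 and 7 in Protocol 4.2 carry the same exception. One of the reasons for stopping study AR101 in Protocol 4.4.1 is "Subject desires to receive commercially available product".

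**What is recorded.** The current treatment plan is asked at months 3, 6 and 9 and again at Study Exit, in every pathway (Protocol 7.1.6–7.1.7 and the matching sections for Pathways 2 to 5).

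**What is summarised.** SPT is presented "for change from baseline to Study Exit visit by years of total AR101 exposure including parent studies and overall" (SAP 11.2). Immunoglobulins are summarised by time point and exposure years, separately for Pathways 1–3, 4 and 5, with change from baseline to Study Exit on the log10 scale (SAP 11.1, 6.3). SAP 6.2 plans no stratification, and SAP 4 defines only the Safety Population.

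**The concern.** In this study the last dose of AR101 means the last study-supplied dose: SAP 7.4 starts the follow-up period on the day after the last dose of study product. AR101 is also the marketed product (Protocol 1.1). A subject who moves to it at End of Treatment is still on AR101 at Study Exit, and one on food-equivalent oral immunotherapy is still receiving peanut allergen. A subject who is avoiding peanut without immunotherapy is off treatment. The planned Study Exit rows do not separate these subjects.

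At stake is whether the tables can answer the part of the exploratory objective that concerns the time after the last dose. A row placed 12 months after the last dose invites reading as an off-treatment result. If continuers hold their immunologic changes better than those who stop, the pooled row will look more like persistence than the off-treatment subjects alone would. Protocol 11.2 gives some reason to expect a difference, since investigators must tell families that dosing has to continue for desensitization to be maintained.

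**Working it through.** There is no planned figure to reproduce. Protocol 9.1 states "There is no sample size calculation for this study", and all results are descriptive.

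**Step 1. Does any planned split separate the groups?**
- *Years of total AR101 exposure:* SAP 9.11 builds exposure from in-clinic doses and the Study Product Exposure page, with parent-study time added. Nothing shows that commercial AR101 after End of Treatment is counted.
- *Pathway group:* this reflects parent study and earlier allocation, not follow-up treatment.
- *Concomitant medication:* SAP 9.12 classes anything begun after the last study dose as concomitant. It is tabulated by drug class and not linked to Study Exit outcomes.
- *Current treatment plan:* it appears in the SAP only in the design description (2.4.2.7).

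None of them does.

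**Step 2. What can a pooled row tell us?** Let q be the share still on immunotherapy at Study Exit and r the fraction of the End of Treatment effect kept by those who are off it. Assume continuers keep all of the effect and that both groups had the same mean effect at End of Treatment. Then

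pooled retention R = q × 1 + (1 − q) × r.

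Both q and r are assumptions, because the documents give neither.

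| | q = 0 | q = 0.25 | q = 0.50 | q = 0.75 | q = 0.90 |
|---|---|---|---|---|---|
| r = 0 | 0% | 25% | 50% | 75% | 90% |
| r = 0.5 | 50% | 62.5% | 75% | 87.5% | 95% |
| r = 1 | 100% | 100% | 100% | 100% | 100% |

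Solving for the quantity of interest gives r = (R − q)/(1 − q). For an observed R of 0.75:
- q = 0: r = 0.75
- q = 0.50: r = 0.25/0.50 = 0.50
- q = 0.75: r = 0/0.25 = 0

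The same pooled row is compatible with three-quarters, half or none of the effect surviving without treatment. R equals r only if nobody continues or nothing is lost.

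**Step 3. Is change from baseline the right contrast?** SAP 7.4 defines baseline as the last value before the first AR101 dose in ARC008. Pathways 1, 2 and 4 enter after AR101 treatment in the parent study, so their baseline is already a treated value. Splitting the change,

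(Study Exit − baseline) = (End of Treatment − baseline) + (Study Exit − End of Treatment),

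only the last term describes what happens after study treatment stops. An SPT subject in these pathways who loses effect could show a positive change from baseline; one who loses none would show whatever was gained during ARC008. SAP 11.1 and 11.2 plan no change from End of Treatment to Study Exit. Grouping by follow-up treatment alone would therefore not be enough for these pathways.

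**The case against.** The strongest reply is that the affected rows are not where the plan places its clinical question. Sustained clinical effect belongs to the food challenges: Protocol 3.4.2 gives the optional double-blind challenge after the follow-up year the task of assessing continued desensitization, and treats the immunoglobulins as possible surrogates. That challenge is only listed; SAP 10.1 summarises the open-label challenges and the End of Treatment double-blind challenge. A reader might infer that the plan produces a biased clinical result on sustained effect. It does not, because there is no planned pooled clinical summary at Study Exit to be biased. This stands, and it limits the point to SPT and immunoglobulins.

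A reader might also infer that most subjects will be on commercial AR101 at Study Exit. The documents do not support that. Under Protocol 3.2.6, commercial access alone brings End of Treatment for US subjects from ARC007 and ARC011, and may do so for US subjects from ARC002 and ARC004 if the sponsor directs. For the rest, availability is an added condition to about 3 or 5 years of treatment. Access is not use, and no counts are given. Protocol 6.3 also trains subjects in a strict elimination diet at End of Treatment unless instructed otherwise. That does not remove the concern, since Protocol 1.1 says the marketed product is itself used with a peanut-avoidant diet.

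Finally, the data are not hidden. SAP 7.2 puts collected data in listings unless otherwise noted, SAP 6.1 allows further exploratory analyses, and the table shells are not available here. All true, but a reader of the listings would have to join treatment plan to outcome subject by subject. The SAP text itself plans no such analysis.

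**Conclusion.** The point holds for the Study Exit summaries of SPT (SAP 11.2) and immunoglobulins (SAP 11.1). As planned, they may combine on-treatment and off-treatment values with no means of telling them apart. The off-treatment effect, which their objective includes, cannot be identified from them.

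The size of any distortion is unknown, because the documents do not give the share of subjects in each follow-up group. The retention figures above show only that the effect is not identified. They rest on assumed q and r, on continuers keeping the whole effect, and on equal effects at End of Treatment. The direction, towards apparent persistence, depends on continuers holding their changes better than the others; the documents do not establish this for each immunoglobulin measure.

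These are exploratory, descriptive summaries in a study without hypothesis tests, and the SAP does not label them off-treatment or sustained. The correction is worth making, but the primary safety objective does not depend on it.

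**What to change.** 1. From the treatment plan recorded at months 3, 6, 9 and Study Exit, derive follow-up groups: no peanut immunotherapy at any contact; commercial AR101; food-equivalent or other immunotherapy; mixed or unknown.
2. Present Study Exit SPT and immunoglobulin values by group with n, together with any Study Exit double-blind challenge results that are shown.
3. Add the change from End of Treatment to Study Exit, since change from the ARC008 baseline does not isolate the follow-up year in Pathways 1, 2 and 4.
4. Limit any statement about effect after stopping AR101 to the no-immunotherapy group. State that the groups are self-selected, that they include early discontinuers, and that four contacts do not verify intake between them.
5. SAP 1.1 records that Version 2 was written after database lock, with changes confined to Appendix A. If added at this stage, identify the analysis as post hoc, as SAP 6.1 requires.

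The cost is one extra derivation from data already collected, and smaller cells. Cell sizes cannot be foreseen: SAP 7.7 says the study ended much earlier than expected, and the number reaching Study Exit is not given.
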